10.4 Statistical Analyses

For continuous variables, descriptive summaries will display number of subjects, arithmetic mean, geometric mean (as appropriate), standard deviation, median, minimum, and maximum by treatment group. For categorical variables, counts and percentages will be displayed.

In general, missing data will not be imputed with the exception that for the ITT analysis, missing viral load results will be imputed using the last-observation-carried-forward (LOCF) methodology.

Additional details regarding statistical methods will be provided in the Statistical Analysis Plan.

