5.2 Handling of Missing Data

5.2.1 Missing Efficacy Endpoints

Missing data will be replaced for the efficacy endpoint in the ITT analyses using the Last observation carried forward (LOCF) method.

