5.5.2 Analysis of Secondary Efficacy Endpoints

The following 6 secondary efficacy endpoints will be summarized using descriptive statistics by visit, as appropriate:

- log10-transformed Viral load as measured in saliva by RT-qPCR at each visit by RT-qPCR
- proportion of subjects with $\geq 95\%$ reduction in SARS-CoV-2 viral load by RT-qPCR at each visit
- time to clearance of viral infection in saliva via RT-qPCR
- proportion of subjects demonstrating clearance of viral infection via RT-qPCR at Day 8/ET visit
- COVID-19 composite severity score at each visit
- time to alleviation of COVID-19 symptoms, defined as the number of hours from the first dose to the first time when all eight symptoms had been assessed by the subject as none (0) or mild (1)
- time to sustained alleviation of COVID-19 symptoms, defined the number of hours from the first dose to the time when all eight symptoms had been assessed by the subject as none (0) or mild (1) and no single symptom reoccurs later at a level above mild (1).

Both time to alleviation of COVID-19 symptoms and time to sustained alleviation of COVID-19 symptoms will be derived from self-assessment by study subjects and recorded on the subjects' diary cards.

For log10-transformed viral load data, geometric means will be computed by exponentiating (base 10) the group means of the log10-transformed viral load. Time-to-event variables will be evaluated using the Kaplan-Meier method and p-values for treatment comparison will be provided via log rank test.

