Note 1: Clearance of viral infection in saliva is defined as a negative test (Ct value ≥ 32) via RT-qPCR, i.e. achievement of [1] RP Ct =0, AND [2] Average N1 Ct =32 or Average N1 Ct ='Undetermined'. Subjects who did not achieve clearance at the last assessment of the study are considered censored at the time of the last assessment.

Note 2: Subjects who did not achieve clearance at the exit of study are considered censored.

Note 3: Percentiles and 95% CI of median are derived using the Kaplan-Meier method. P-values for treatment comparison are from Log Rank Test.

Source: Listing 16.2.6.4, 16.2.5.3

O:\Studies\EmitBio\EB-P12-01\Biometrics\Programs\Tables\xxx.sas ran on Month Day, Year at hh:mm on data from Month Day, Year.

Figure 15.1.1 - Kaplan-Meier Plot of Time to Clearance of Viral Infection for Intent-to-Treat Population

Figure 15.1.2 - Kaplan-Meier Plot of Time to Clearance of Viral Infection for Per-Protocol Population

Table 14.2.4 – COVID-19 Composite Severity Score by Visit

Population	Study Visit	Category	Statistics	4 Days RD-X19	7 Days RD-X19	Sham
Intent-to-Treat	Visit 1 /Day 1 (Baseline)	Actual Value	N	XX	XX	XX
			Mean \pm SD	XX.X \pm XX.X	XX.X \pm XX.X	XX.X \pm XX.X
			Median	XX.X	XX.X	XX.X
		Actual Value	Min, Max	XX, XX	XX, XX	XX, XX
			N	XX	XX	XX
	Visit 5 /Day 8	Actual Value	Mean \pm SD	XX.X \pm XX.X	XX.X \pm XX.X	XX.X \pm XX.X
			Median	XX.X	XX.X	XX.X
			Min, Max	XX, XX	XX, XX	XX, XX
		Change from Baseline	Mean \pm SD	XX.X \pm XX.X	XX.X \pm XX.X	XX.X \pm XX.X
			Median	XX.X	XX.X	XX.X
Per-Protocol	Visit 1 /Day 1 (Baseline)	Actual Value	Min, Max	XX, XX	XX, XX	XX, XX
			N	XX	XX	XX
			Mean \pm SD	XX.X \pm XX.X	XX.X \pm XX.X	XX.X \pm XX.X
		Actual Value	Median	XX.X	XX.X	XX.X
			Min, Max	XX, XX	XX, XX	XX, XX
	Visit 5 /Day 8	Actual Value	N	XX	XX	XX
			Mean \pm SD	XX.X \pm XX.X	XX.X \pm XX.X	XX.X \pm XX.X
			Median	XX.X	XX.X	XX.X
		Change from Baseline	Min, Max	XX, XX	XX, XX	XX, XX
			Mean \pm SD	XX.X \pm XX.X	XX.X \pm XX.X	XX.X \pm XX.X
			Median	XX.X	XX.X	XX.X
			Min, Max	XX, XX	XX, XX	XX, XX

Note: Missing data will be replaced for the efficacy endpoint in the ITT analyses using the Last observation carried forward (LOCF) method.

Source: Listing 16.2.6.1

O:\Studies\EmitBio\EB-P12-01\Biometrics\Programs\Tables\xxx.sas ran on Month Day, Year at hh:mm on data from Month Day, Year.

Table 14.2.5.1 – Time to Alleviation of COVID-19 Symptoms

Population	Statistics	4 Days RD-X19	7 Days RD-X19	Sham
Intent-to-Treat	N	XX	XX	XX

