				Date (Study Day)	Time					
Treatment:										

Study Day is calculated relative to date of first treatment. Day 1 is the day of first treatment.

O:\Studies\ EmitBio\EB-P12-01\Biometrics\Programs\Listings\xxx.sas ran on Month Day, Year at hh:mm on data from Month Day, Year

Listing 16.2.6.4 – Derived Clearance of Viral Infection and Time-Weighted Average Change from Baseline in Log10-Transformed Viral Load via RT-qPCR

Subject	Cohort	Analysis	Clearance of Viral Infection (Study Day)				Change from Baseline in Log10-Transformed Viral Load (Study Day)			TWA Change from Day 1 to Day 8
			Visit 2 /Day 2	Visit 3 /Day 3	Visit 4 /Day 5	Visit 5 /Day 8	Visit 3 /Day 3	Visit 4 /Day 5	Visit 5 /Day 8	
Treatment:										
	ITT		No (2)	No (3)	No (5)	No (9)	xx.x (3)	xx.x (5)	xx.x (9)	xx.x
	PP		No (2)	No (3)		No (9)	xx.x (3)		xx.x (9)	xx.x

Abbreviation: ITT = Intent-to-Treat, PP = Per-Protocol, TWA = Time-Weighted Average, LOCF = Last observation carried forward
Study Day is calculated relative to date of first treatment. Day 1 is the day of first treatment.

For the ITT analysis, missing viral load will be imputed using the LOCF method.

Note 1: Clearance of viral infection is defined, based on viral load via RT-qPCR, as achievement of: [1] RP Ct ≥ 0 , AND [2] Average N1 Ct ≥ 32 or Average N1 Ct = “Undetermined”.

Note 2: TWA Change from Day 1 to Day 8 is calculated using the trapezoidal rule.

O:\Studies\ EmitBio\EB-P12-01\Biometrics\Programs\Listings\xxx.sas ran on Month Day, Year at hh:mm on data from Month Day, Year

Listing 16.2.7 - Adverse Events

Subject	Cohort	AE No.	System Organ Class / Preferred Term / Event Name	Occurred prior to first dose?	Start Date (Study Day)	Stop Date (Study Day)	Serious AE?	Intensity	Causality to Study Device	Action Taken	Outcome
Treatment:											

Note: Adverse events coded in MedDRA, version xx.x

Study Day is calculated relative to date of first treatment. Day 1 is the day of first treatment while Day -1 is the day prior to first treatment.

O:\Studies\EmitBio\EB-P12-01\Biometrics\Programs\Listings\xxx.sas ran on Month Day, Year at hh:mm on data from Month Day, Year

Listing 16.2.8.1 – Out-of-Range Results of Clinical Laboratory Tests

Subject	Cohort	Visit	Lab Panel	Test Name	Result	Flag	Out of Range: NCS or CS
---------	--------	-------	-----------	-----------	--------	------	-------------------------

Treatment:

Abbreviation: CS = clinically significant, NCS = not clinically significant

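### The SAP's LOCF rule reaches ITT clearance status and is not reconciled with the censoring rule for time to clearance, so early leavers could be kept at risk to Day 8

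*Combined protocol and SAP*

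**What the plan says.** **Carry-forward.** SAP 5.2.1 states: "Missing data will be replaced for the efficacy endpoint in the ITT analyses using the Last observation carried forward (LOCF) method". No endpoint is exempted. Protocol 10.4 is narrower: "missing viral load results will be imputed using the last-observation-carried-forward (LOCF) methodology".

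**Derivation listing.** SAP Listing 16.2.6.4 holds both the derived clearance status and the time-weighted average change. Its footnote reads "For the ITT analysis, missing viral load will be imputed using the LOCF method". The clearance cells of the ITT example row run "No (2) No (3) No (5) No (9", with the study day in brackets. The Per-Protocol row beneath is the same except that its Visit 4/Day 5 cell is empty.

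**Analysis.** SAP 5.5.2 says: "Time-to-event variables will be evaluated using the Kaplan-Meier method and p-values for treatment comparison will be provided via log rank test". Table 14.2.3 reports time to clearance and cites its data as "Source: Listing 16.2.6.4, 16.2.5.3". The second of these is the treatment application log.

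**Censoring.** Note 1 to Table 14.2.3 says: "Subjects who did not achieve clearance at the last assessment of the study are considered censored at the time of the last assessment". Note 2 adds, without giving a time: "Subjects who did not achieve clearance at the exit of study are considered censored".

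**The concern.** Kaplan-Meier and log-rank methods already deal with incomplete follow-up. A subject counts in the risk set until last observed and is then censored. Carrying a *not cleared* status forward adds follow-up time during which no sample exists and no clearance can be seen. It creates no events, but it enlarges the later risk sets and so pulls estimated clearance down.

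The SAP leaves room for this. The filled ITT cell in Listing 16.2.6.4 receives both a status and a study day, and the listing does not flag imputed cells. Table 14.2.3 draws on this derived listing and does not cite the sample-level Listing 16.2.6.3. A programmer who takes the last assessment from the ITT row could therefore pick up a visit that never took place.

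Two kinds of subject would be affected:

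- **Early leavers without an early-termination sample.** Protocol 8.5.2 places them under no obligation to return, and 8.5.3 does not replace subjects who withdraw or are lost after device use.
- **Subjects whose later samples are unusable.** SAP 5.5 excludes inconclusive quantitations and samples with an undetermined RNase P control. If these are then treated as missing, a *not cleared* result from Day 5 could be written in at Day 8.

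At stake are the ITT medians, log-rank p-values and day-8 estimates in Table 14.2.3, and the ITT curve in Figure 15.1.1.

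**Working it through.** The documents give no clearance rate, dropout rate or power figure for this endpoint, so there is no planned number to reproduce. All rates below are assumptions.

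**Step 1. Does LOCF reach clearance status?** Yes. SAP 5.2.1 has no exception, the listing carries the LOCF footnote, and the Day 5 clearance cell is filled in ITT only.

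**Step 2. Does the example row show a changed survival time?** No. Both rows end with a Day 9 result of not cleared, so the subject is censored at Day 9 with or without the filled Day 5 cell. Only a gap with no usable later sample changes the time.

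**Step 3. Size within one arm.** Assume 20% clear by Day 3, 40% of the remainder by Day 5, and 50% of those still left by Day 8. Let *L* be the share of subjects uncleared at Day 3 who leave then, independently of later clearance.

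- True clearance by Day 8: 0.20 + 0.80 × (1 − 0.60 × 0.50) = 0.20 + 0.80 × 0.70 = 76%. Censoring at the last real sample estimates this for any *L*.
- With LOCF to Day 8: 0.20 + 0.80 × (1 − *L*) × 0.70.

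| *L* | LOCF to Day 8 | Censored at last sample |
|---|---|---|
| 10% | 70.4% | 76% |
| 15% | 67.6% | 76% |
| 20% | 64.8% | 76% |

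**Step 4. Size between arms.** Simulation with the same clearance rates, no device effect, and 20 v 20 subjects (one device dose against the pooled sham group, 10 + 10). A hazard ratio above 1 means apparently faster clearance on the device. Rejection is the share of log-rank tests with p < 0.05.

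| Loss, device v sham | Hazard ratio under LOCF | Rejection |
|---|---|---|
| 10% v 10% | 1.00 | 5.4% |
| 20% v 20% | 1.00 | 5.2% |
| 0% v 5% | 1.08 | 5.4% |
| 0% v 10% | 1.16 | 6.3% |
| 10% v 20% | 1.16 | 6.4% |
| 0% v 20% | about 1.35 | 9.8% |

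With censoring at the last sample, the 0% v 20% case gives a hazard ratio of 1.00 and rejection of about 5%.

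**Step 5. A single small dataset.** Take one cohort of 20 device and 10 sham subjects. Suppose 2, 4 and 6 device subjects and 0, 1 and 2 sham subjects clear at Days 3, 5 and 8. Under LOCF the uncleared proportions at Day 8 are 0.400 and 0.700, with p = 0.116, however many uncleared subjects left after Day 3. Censoring those leavers at Day 3 gives:

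| Leavers, device / sham | Uncleared at Day 8, device / sham | Log-rank p |
|---|---|---|
| 1 / 0 | 0.371 / 0.700 | 0.090 |
| 0 / 1 | 0.400 / 0.667 | 0.165 |
| 2 / 1 | 0.338 / 0.667 | 0.098 |
| 4 / 2 | 0.257 / 0.625 | 0.076 |
| 4 / 0 | 0.257 / 0.700 | 0.030 |
| 0 / 2 | 0.400 / 0.625 | 0.235 |

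The p-value can move either way.

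**The case against.** The strongest reply is that the SAP already has the right rule. Note 1 to Table 14.2.3 is specific to this endpoint, and in ordinary usage an assessment is a sample that was taken. The pattern of footnotes agrees: Tables 14.2.1.1, 14.2.2.1, 14.2.2.3 and 14.2.4 each print the LOCF note, while the time-to-event shells 14.2.3, 14.2.5.1 and 14.2.5.2 print censoring notes and no LOCF note. The example row is also weak evidence of how times are derived. It shows an intermittent gap, and it prints a Day 2 clearance status in both rows although no viral specimen is taken that day.

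Much of this stands. A reader might infer that the SAP definitely keeps early leavers at risk to Day 8. The documents do not support that, since no section says so and Note 1 points the other way. But neither does any section say that a carried-forward visit is not an assessment, and the listing that feeds the table fills such visits.

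Three further limits also stand:

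- A real early-termination sample is assigned to the nearest scheduled visit (SAP 5.1), so only subjects without a usable later sample are affected.
- Figure 15.1.2 is Per-Protocol, where LOCF is not specified, so it is not affected.
- A reader might expect imputation to drive the ITT and Per-Protocol curves apart. The Per-Protocol population admits only subjects who complete the study, so for early leavers the contrast is mainly one of populations.

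**Conclusion.** The point holds as an unresolved conflict between the LOCF rule (SAP 5.2.1 and Listing 16.2.6.4) and the censoring rule in Table 14.2.3 Note 1. If Note 1 is applied to real samples, the effect is zero. If carried-forward visits count as assessments, ITT clearance by Day 8 falls from 76% to between 70.4% and 64.8% for 10% to 20% loss, on the assumed clearance rates and non-informative loss. The between-arm bias depends on the difference in loss: about nil when loss is equal, a hazard ratio of about 1.16 at 10 points and about 1.35 at 20 points. The last figure needs all the loss to fall in one arm and should be read as an extreme.

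Severity is minor to moderate. Time to clearance is a secondary endpoint in a hypothesis-generating study of convenience size, SAP 5.1 calls its p-values descriptive, and Table 14.2.3 is not among the interim tables.

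**What to change.** - In SAP 5.2.1, Listing 16.2.6.4 and Table 14.2.3, state that LOCF is not applied to time to clearance.
- In Table 14.2.3 Note 1, define the last assessment as the last analysis-qualified sample actually collected, and censor uncleared subjects on that date. Align Note 2 with it or delete it.
- In Listing 16.2.6.4, leave clearance cells blank where there is no sample, remove the Visit 2/Day 2 clearance column, and show the Day 1 status, which is needed to apply the table's exclusion of subjects already clear at baseline.
- State separately whether LOCF applies to the proportion cleared at Day 8/ET, which is a different endpoint.

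The cost is SAP and shell wording plus one programming change. No new data are needed.

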5.5.2 Analysis of Secondary Efficacy Endpoints

The following 6 secondary efficacy endpoints will be summarized using descriptive statistics by visit, as appropriate:

- log10-transformed Viral load as measured in saliva by RT-qPCR at each visit by RT-qPCR
- proportion of subjects with $\geq 95\%$ reduction in SARS-CoV-2 viral load by RT-qPCR at each visit
- time to clearance of viral infection in saliva via RT-qPCR
- proportion of subjects demonstrating clearance of viral infection via RT-qPCR at Day 8/ET visit
- COVID-19 composite severity score at each visit
- time to alleviation of COVID-19 symptoms, defined as the time when all eight symptoms had been assessed by the subject as none (0) or mild (1).

For log10-transformed viral load data, geometric means will be computed by exponentiating (base 10) the group means of the log10-transformed viral load. Time-to-event variables will be evaluated using the Kaplan-Meier method.

Revised Text and Location

5.5.2 Analysis of Secondary Efficacy Endpoints

The following **7** secondary efficacy endpoints will be summarized using descriptive statistics by visit, as appropriate:

- log10-transformed Viral load as measured in saliva by RT-qPCR at each visit by RT-qPCR
- proportion of subjects with $\geq 95\%$ reduction in SARS-CoV-2 viral load by RT-qPCR at each visit
- time to clearance of viral infection in saliva via RT-qPCR
- proportion of subjects demonstrating clearance of viral infection via RT-qPCR at Day 8/ET visit
- COVID-19 composite severity score at each visit
- time to alleviation of COVID-19 symptoms, defined as the number of hours from the first dose to the first time when all eight symptoms had been assessed by the subject as none (0) or mild (1)
- time to sustained alleviation of COVID-19 symptoms, defined the number of hours from the first dose to the time when all eight symptoms had been assessed by the subject as none (0) or mild (1) and no single symptom reoccurs later at a level above mild (1).

Both time to alleviation of COVID-19 symptoms and time to sustained alleviation of COVID-19 symptoms will be derived from self-assessment by study subjects and recorded on the subjects' diary cards.

For log10-transformed viral load data, geometric means will be computed by exponentiating (base 10) the group means of the log10-transformed viral load.

Time-to-event variables will be evaluated using the Kaplan-Meier method and p-values for treatment comparison will be provided via log rank test.

2. Original Text and Location

Interim Analysis

Upon completion of all subjects in Cohort 1, an unblinded interim analysis will be conducted focusing on the following evaluations:

- Efficacy:
 - Geometric mean viral load as measured in saliva on day 1, 3, 5 and 8 by RT-qPCR
 - Proportion of subjects demonstrating viral load reduction $\geq 95\%$ on day 3, 5 and 8 by RT-qPCR.
- Safety:
 - All safety tabulations as listed in section 5.6.1 will be assessed as part of the interim analysis.

- Summary or Treatment Emergent Adverse Events including a review of listings to monitor:
 - Number of subjects experiencing laryngospasm, bronchospasm or anaphylaxis within 2 hours after use of the RD-X19 Device that is considered related to RD-X19.
 - Number of subjects experiencing an allergic reaction such as generalized urticaria (defined as occurring at three or more body parts) within 72 hours after use of study treatment that is considered related to RD-X19.
 - Number of subjects experiencing SAE or Grade 3 AE, in the same SOC grouping of PT, considered to be related to RD-X19.

As study subjects in cohort 1 are essentially a separate study, there is no prohibition to sponsor being unblinded for the interim analysis. Cohort 1 subjects are not tied to cohort 2 in any way and unblinding data from cohort 1 has no operational or statistical implications for cohort 2 assessment by sponsor. Study site personnel may not be unblinded to cohort 1 as there is a reasonable possibility that this information could be the basis for bias in the assessment of cohort 2.

To meet above review interest, the following summary tables (treatment groups: 4 Days RD-X19 vs. Sham) and by-subject data listings will be prepared for the interim analysis:

Tables / Listing	Description	Population
Efficacy		
Table 14.2.2.1	Log10-Transformed Viral Load via RT-qPCR by Visit	ITT Population of Cohort 1
Table 14.2.2.3	Proportion of Subjects with At Least 95% Reduction by Visit in SARS-CoV-2 Viral Load via RT-qPCR	ITT Population of Cohort 1
Safety		
Table 14.3.1.1	Treatment-Emergent Adverse Events by System Organ Class and Preferred Term	Safety Population of Cohort 1
Table 14.3.1.2	Treatment-Emergent Adverse Events by System Organ Class, Preferred Term and Severity	Safety Population of Cohort 1
Table 14.3.1.3	Treatment-Emergent Adverse Events by System Organ Class, Preferred Term and Causality to Study Device	Safety Population of Cohort 1
Table 14.3.2	Reactogenicity by Visit	Safety Population of Cohort 1
Table 14.3.3	Oropharyngeal assessment by Visit	Safety Population of Cohort 1
Listing 16.2.7	Adverse Events	Cohort 1 subjects
Listing 16.2.9.1	Reactogenicity Assessment	Cohort 1 subjects
Listing 16.2.9.2	Oropharyngeal Assessment	Cohort 1 subjects

Revised Text and Location

Interim Analysis

Upon completion of all subjects in Cohort 1, an unblinded interim analysis will be conducted focusing on the following evaluations:

- Efficacy:
 - Geometric mean viral load as measured in saliva on day 1, 3, 5 and 8 by RT-qPCR
 - Proportion of subjects demonstrating viral load reduction $\geq 95\%$ on day 3, 5 and 8 by RT-qPCR.
 - **Time to alleviation of COVID-19 signs and symptoms**
 - **Time to sustained alleviation of COVID-19 signs and symptoms**
- Safety:
 - All safety tabulations as listed in section 5.6.1 will be assessed as part of the interim analysis.
 - Summary or Treatment Emergent Adverse Events including a review of listings to monitor:
 - **Number of study subjects experiencing any Serious Adverse Reaction (SAE).**
 - **Number of study subject experiencing treatment site reactions, including pain, induration or erythema of the oropharynx or oral mucosa, including the uvula and tongue.**
 - **Number of study subjects with any laboratory result that is out-of-range using the testing laboratory's institutional standards, including blood, urine and methemoglobin measured by pulse oxymetry.**
 - **Number of subjects experiencing laryngospasm, bronchospasm or anaphylaxis within 2 hours after use of the RD-X19 Device that is considered related to RD-X19.**
 - **Number of subjects experiencing an allergic reaction such as generalized urticaria (defined as occurring at three or more body parts) within 72 hours after use of study treatment that is considered related to RD-X19.**
 - **Number of subjects experiencing Grade 3 TEAE, in the same SOC grouping of PT, considered to be related to RD-X19.**

As study subjects in cohort 1 are essentially a separate study, there is no prohibition to sponsor being unblinded for the interim analysis. Cohort 1 subjects are not tied to cohort 2 in any way and unblinding data from cohort 1 has no operational or statistical implications for cohort 2 assessment by sponsor. Study site personnel may not be unblinded to cohort 1 as there is a reasonable possibility that this information could be the basis for bias in the assessment of cohort 2.

To meet above review interest, the following summary tables (treatment groups: 4 Days RD-X19 vs. Sham) and by-subject data listings will be prepared for the interim analysis:

Tables / Listing	Description	Population
Efficacy		
Table 14.1.3	Demographic and Baseline Characteristics	Safety Population Cohort 1
Table 14.2.1.1	Time-Weighted Average Change in Log10-Transformed Viral Load by RT-qPCR from Baseline to Day 8	ITT Population of Cohort 1
Table 14.2.2.1	Log10-Transformed Viral Load via RT-qPCR by Visit	ITT Population of Cohort 1
Table 14.2.2.3	Proportion of Subjects with At Least 95% Reduction by Visit in SARS-CoV-2 Viral Load via RT-qPCR	ITT Population of Cohort 1
Table 14.2.5.1	Time to Alleviation of COVID-19 Symptoms	ITT Population of Cohort 1
Table 14.2.5.2	Time to Sustained Alleviation of COVID-19 Symptoms	ITT Population of Cohort 1
Safety		
Table 14.3.1.1	Treatment-Emergent Adverse Events by System Organ Class and Preferred Term	Safety Population of Cohort 1
Table 14.3.1.2	Treatment-Emergent Adverse Events by System Organ Class, Preferred Term and Severity	Safety Population of Cohort 1
Table 14.3.1.3	Treatment-Emergent Adverse Events by System Organ Class, Preferred Term and Causality to Study Device	Safety Population of Cohort 1
Table 14.3.2	Reactogenicity by Visit	Safety Population of Cohort 1
Table 14.3.3	Oropharyngeal assessment by Visit	Safety Population of Cohort 1
Listing 16.2.7	Adverse Events	Cohort 1 subjects
Listing 16.2.8.1	Out-of-Range Results of Clinical Laboratory Tests	Cohort 1 subjects
Listing 16.2.9.1	Reactogenicity Assessment	Cohort 1 subjects
Listing 16.2.9.2	Oropharyngeal Assessment	Cohort 1 subjects
Listing 16.2.9.6	Methemoglobin Measurement	Cohort 1 subjects

3. Original Summary Table 14.2.3

Table 14.2.3 – Clearance of Viral Infection in Saliva via RT-qPCR

Population	Endpoint	Statistics	4 Days RD-X19	7 Days RD-X19	Sham
Intent-to-Treat	Time to Clearance of Viral Infection	N	XX	XX	XX
		n (%) Censored	XX (XX.X)	XX (XX.X)	XX (XX.X)
		Median of Time	XX.X	XX.X	XX.X
		25 th , 75 th Percentiles	XX.X, XX.X	XX.X, XX.X	XX.X, XX.X
		95% CI of Median	(XX.X, XX.X)	(XX.X, XX.X)	(XX.X, XX.X)
	Subjects Demonstrating Clearance of Viral Infection at Day 8/ET Visit	n (%)	XX (XX.X)	XX (XX.X)	XX (XX.X)
Per-Protocol	Time to Clearance of Viral Infection	N	XX	XX	XX
		n (%) Censored	XX (XX.X)	XX (XX.X)	XX (XX.X)
		Median of Time	XX.X	XX.X	XX.X
		25 th , 75 th Percentiles	XX.X, XX.X	XX.X, XX.X	XX.X, XX.X
		95% CI of Median	(XX.X, XX.X)	(XX.X, XX.X)	(XX.X, XX.X)
	Subjects Demonstrating Clearance of Viral Infection at Day 8/ET Visit	n (%)	XX (XX.X)	XX (XX.X)	XX (XX.X)

Abbreviation: CI = Confidence Interval

Note 1: Clearance of viral infection in saliva is defined as a negative test (Ct value ≥ 32) via RT-qPCR.

Note 2: Subjects who did not achieve clearance at the exit of study are considered censored.

Note 3: Percentiles and 95% CI of median are derived using the Kaplan-Meier method.

Source: Listing 16.2.6.4

O:\Studies\EmiT Bio\EB-P12-01\Biometrics\Programs\Tables\xxx.sas ran on Month Day, Year at hh:mm on data from Month Day, Year.

Revised Summary Table and Added Figures

Table 14.2.3 – Clearance of Viral Infection in Saliva via RT-qPCR

Population	Endpoint	Statistics	4 Days RD-X19	7 Days RD-X19	Sham
Intent-to-Treat	Time to Clearance of Viral Infection	N	XX	XX	XX
		n (%) Censored	XX (XX.X)	XX (XX.X)	XX (XX.X)
		Median of Time	XX.X	XX.X	XX.X
		25 th , 75 th Percentiles	XX.X, XX.X	XX.X, XX.X	XX.X, XX.X
		95% CI of Median	(XX.X, XX.X)	(XX.X, XX.X)	(XX.X, XX.X)
		P-value RX-X19 vs. Sham	0.XXX	0.XXX	
	Subjects Demonstrating Clearance of Viral Infection at Day 8/ET Visit	n (%)	XX (XX.X)	XX (XX.X)	XX (XX.X)
Per-Protocol	Time to Clearance of Viral Infection	N	XX	XX	XX
		n (%) Censored	XX (XX.X)	XX (XX.X)	XX (XX.X)
		Median of Time	XX.X	XX.X	XX.X
		25 th , 75 th Percentiles	XX.X, XX.X	XX.X, XX.X	XX.X, XX.X
		95% CI of Median	(XX.X, XX.X)	(XX.X, XX.X)	(XX.X, XX.X)
		P-value RX-X19 vs. Sham	0.XXX	0.XXX	
	Subjects Demonstrating Clearance of Viral Infection at Day 8/ET Visit	n (%)	XX (XX.X)	XX (XX.X)	XX (XX.X)

Abbreviation: CI = Confidence Interval

Subjects with clearance of viral infection at baseline are excluded from the analysis of time-to-clearance of viral infection.

Note 1: Clearance of viral infection in saliva is defined as a negative test via RT-qPCR, i.e. achievement of [1] RP Ct =0, AND [2] Average N1 Ct =32 or Average N1 Ct ='Undetermined'. Subjects who did not achieve clearance at the last assessment of the study are considered censored at the time of the last assessment.

Note 2: Percentiles and 95% CI of median are derived using the Kaplan-Meier method. P-values for treatment comparison are from Log Rank Test.

Source: Listing 16.2.6.4, 16.2.5.3

O:\Studies\EmitBio\EB-P12-01\Biometrics\Programs\Tables\xxx.sas ran on Month Day, Year at hh:mm on data from Month Day, Year.

Figure 15.1.1 - Kaplan-Meier Plot of Time to Clearance of Viral Infection for Intent-to-Treat Population

Figure 15.1.2 - Kaplan-Meier Plot of Time to Clearance of Viral Infection for Per-Protocol Population

4. Original Summary Table 14.2.5

Table 14.2.5 – Time to Alleviation of COVID-19 Symptoms

Population	Statistics	4 Days RD-X19	7 Days RD-X19	Sham
Intent-to-Treat	N	XX	XX	XX
	n (%) Censored	XX (XX.X)	XX (XX.X)	XX (XX.X)
	Median of Time	XX.X	XX.X	XX.X
	25 th , 75 th Percentiles	XX.X, XX.X	XX.X, XX.X	XX.X, XX.X
	95% CI of Median	(XX.X, XX.X)	(XX.X, XX.X)	(XX.X, XX.X)
Per-Protocol	N	XX	XX	XX
	n (%) Censored	XX (XX.X)	XX (XX.X)	XX (XX.X)
	Median of Time	XX.X	XX.X	XX.X
	25 th , 75 th Percentiles	XX.X, XX.X	XX.X, XX.X	XX.X, XX.X
	95% CI of Median	(XX.X, XX.X)	(XX.X, XX.X)	(XX.X, XX.X)

Abbreviation: CI = Confidence Interval

Note 1: Alleviation of COVID-19 symptoms is defined as all eight symptoms assessed by the subject as none (0) or mild (1).

Note 2: Subjects who did not achieve alleviation at the exit of study are considered censored.

Note 3: Percentiles and 95% CI of median are derived using the Kaplan-Meier method.

Source: Listing 16.2.6.1, 16.2.6.2

O:\Studies\EmiTBio\EB-P12-01\Biometrics\Programs\Tables\xxx.sas ran on Month Day, Year at hh:mm on data from Month Day, Year.

Revised Summary Table and Added Figures

Table 14.2.5.1 – Time to Alleviation of COVID-19 Symptoms

Population	Statistics	4 Days RD-X19	7 Days RD-X19	Sham
Intent-to-Treat	N	XX	XX	XX
	n (%) Censored	XX (XX.X)	XX (XX.X)	XX (XX.X)
	Median of Time	XX.X	XX.X	XX.X
	25 th , 75 th Percentiles	XX.X, XX.X	XX.X, XX.X	XX.X, XX.X
	95% CI of Median	(XX.X, XX.X)	(XX.X, XX.X)	(XX.X, XX.X)
	P-value RX-X19 vs. Sham	0.XXX	0.XXX	
Per-Protocol	N	XX	XX	XX
	n (%) Censored	XX (XX.X)	XX (XX.X)	XX (XX.X)
	Median of Time	XX.X	XX.X	XX.X
	25 th , 75 th Percentiles	XX.X, XX.X	XX.X, XX.X	XX.X, XX.X
	95% CI of Median	(XX.X, XX.X)	(XX.X, XX.X)	(XX.X, XX.X)
	P-value RX-X19 vs. Sham	0.XXX	0.XXX	

Abbreviation: CI = Confidence Interval

Note 1: Alleviation of COVID-19 symptoms is defined as all eight symptoms assessed by the subject as none (0) or mild (1).

Note 2: Time to alleviation is calculated as the number of hours from the first dose to the time of the first occurrence of symptoms alleviation. Subjects who did not achieve alleviation at the last assessment of study are considered censored at the time of the last assessment.

Note 3: Percentiles and 95% CI of median are derived using the Kaplan-Meier method. P-values for treatment comparison are from Log Rank Test.

Source: Listing 16.2.6.1.2, 16.2.5.3

O:\Studies\EmiT Bio\EB-P12-01\Biometrics\Programs\Tables\xxx.sas ran on Month Day, Year at hh:mm on data from Month Day, Year.

Figure 15.2.1 - Kaplan-Meier Plot of Time to Alleviation of COVID-19 Symptoms for Intent-to-Treat Population

Figure 15.2.2 - Kaplan-Meier Plot of Time to Alleviation of COVID-19 Symptoms for Per-Protocol Population

5. New Summary Table and Figures

Table 14.2.5.2 – Time to Sustained Alleviation of COVID-19 Symptoms

Population	Statistics	4 Days RD-X19	7 Days RD-X19	Sham
Intent-to-Treat	N	XX	XX	XX
	n (%) Censored	XX (XX.X)	XX (XX.X)	XX (XX.X)
	Median of Time	XX.X	XX.X	XX.X
	25 th , 75 th Percentiles	XX.X, XX.X	XX.X, XX.X	XX.X, XX.X
	95% CI of Median	(XX.X, XX.X)	(XX.X, XX.X)	(XX.X, XX.X)
	P-value RX-X19 vs. Sham	0.XXX	0.XXX	
Per-Protocol	N	XX	XX	XX
	n (%) Censored	XX (XX.X)	XX (XX.X)	XX (XX.X)
	Median of Time	XX.X	XX.X	XX.X
	25 th , 75 th Percentiles	XX.X, XX.X	XX.X, XX.X	XX.X, XX.X
	95% CI of Median	(XX.X, XX.X)	(XX.X, XX.X)	(XX.X, XX.X)
	P-value RX-X19 vs. Sham	0.XXX	0.XXX	

Abbreviation: CI = Confidence Interval

Note 1: Sustained alleviation of COVID-19 symptoms is defined as all eight symptoms assessed by the subject as none (0) or mild (1) AND no single symptom reoccurs later at a level above mild (1).

Note 2: Time to sustained alleviation is calculated as the number of hours from the first dose to the time of the occurrence of sustained symptoms alleviation.

Subjects who did not

achieve sustained alleviation at the last assessment of the study are considered censored at the time of the last assessment.

Note 3: Percentiles and 95% CI of median are derived using the Kaplan-Meier method. P-values for treatment comparison are from Log Rank Test.

Source: Listing 16.2.6.1.2, 16.2.5.3

O:\Studies\EmiBio\EB-P12-01\Biometrics\Programs\Tables\xxx.sas ran on Month Day, Year at hh:mm on data from Month Day, Year.

Figure 15.3.1 - Kaplan-Meier Plot of Time to Sustained Alleviation of COVID-19 Symptoms for Intent-to-Treat Population

Figure 15.3.2 - Kaplan-Meier Plot of Time to Sustained Alleviation of COVID-19 Symptoms for Per-Protocol Population

6. New Subject Data Listing

Listing 16.2.6.1.2- COVID-19 Symptom Assessment and Severity Score from Subject Diary

Site-Subject	Not Cohort	Done	Day	Assessment										COVID-19 Fever (F)	Severity Score
				Study Day	Date:Time	Cough	Sore Throat	Nasal Congestion	Headache	Chills/ Sweats	Muscle or Joint pain	Fatigue	Nausea		
Treatment:															
xxxx	x		Day 1- Assessment 1		1										
			Day 1- Assessment 2		1										
			Day 2- Assessment 1		2										

COVID-19 Symptom: 0=None, 1=Mild, 2=Moderate, 3=Severe. Study Day is calculated relative to date of first treatment. Day 1 is the day of first treatment.

Note: Assessment at a visit was based on symptoms the subject reports as occurring within the past 3 days of that visit.

O:\Studies\ EmitBio\EB-P12-01\Biometrics\Programs\Listings\xxx.sas ran on Month Day, Year at hh:mm on data from Month Day, Year

Note: The original Listing 16.2.6.1 is changed to Listing 16.2.6.1.1.
